10. STUDY MANAGEMENT

10.1. Ethical approval and subject consent

Subject participation is voluntary. Subject consent will be implied by the subject completing the survey online or via a telephone interview.

As neither GSK nor Concentrics will have any contact with, nor details of, subjects prior to the subject initiating the survey, IRB approval is not deemed necessary.

10.2. Subject confidentiality

Privacy issues will be addressed and respected at each stage of the study. Concentrics will maintain strict confidentiality in handling all HCP identification information. All data provided to GSK will be de-identified; no individual HCP-level data or protected health information will be communicated to GSK.

10.3. Reporting of adverse drug events

See Section [5.3](#).

10.4. Study reporting and publications

A final report will be written and submitted to FDA.

11. APPENDICES**11.1. Screener****PHYSICIAN/PHARMACIST STUDY****PRE-RECRUIT SCREENER**

Thank you for your interest in our research study. I'm _____ with (FIELD AGENCY), and I would like to start by asking you a few questions. Your answers may qualify you to participate in this important research study. May I proceed?

CONTINUE →	YES	1
THANK AND TERMINATE →	NO	2

1) Just to confirm, can you read, speak and understand English?

CONTINUE →	YES	1
TERMINATE →	NO	2

2) Are you currently employed by, or are you a representative of, any of the following?

READ LIST ONE AT A TIME. CIRCLE "NO", "YES" OR "DON'T KNOW" FOR EACH ONE.

		NO	YES	DON'T
A	A pharmaceutical company or manufacturer of medicines or healthcare products	1	2	3
B	Contributor/editor to published guidelines committees for epilepsy or urinary retention	1	2	3
C	Concentrics Research	1	2	3

IF RESPONDENT SAYS “YES” OR “DON’T KNOW (DK)” TO ANY, THEN THANK AND TERMINATE, OTHERWISE CONTINUE.

3) How would you classify your primary specialty? **ALLOW ONE RESPONSE.**

CONTINUE TO Q4 →	Neurology	1
CONTINUE TO Q4 →	Neurosurgery	2
CONTINUE TO Q4 →	Epileptology	3
SKIP TO Q6 →	Pharmacy (Community/Retail)	4
SKIP TO Q6 →	Pharmacy (Hospital/Clinical)	5
TERMINATE →	Other (Specify)	6

IF Q3 = PUNCH 1, 2, OR 3 – ASK Q4.

4) Are you a currently practicing physician? (**IF NEEDED, CLARIFY:** within the past 12 months)

CONTINUE →	YES	1
TERMINATE →	NO	2
TERMINATE →	DON'T KNOW	3

IF Q3 = PUNCH 1, 2, OR 3 – ASK Q5.

5) Do you currently see and treat patients with epilepsy? (**IF NEEDED, CLARIFY:** within the past 12 months)

SKIP TO Q7 →	YES	1
TERMINATE →	NO	2
TERMINATE →	DON'T KNOW	3

IF Q3 = PUNCH 4 OR 5 – ASK Q6.

- 6) Do you currently fill prescriptions for patients with epilepsy? (**IF NEEDED, CLARIFY:** within the past 12 months)

SKIP TO Q8 →	YES	1
TERMINATE →	NO	2
TERMINATE →	DON'T KNOW	3

IF Q3 = PUNCH 1, 2, OR 3, ASK Q7.

- 7) I will now read you a list of medicines. Please tell me all of the medicines, if any, for which you have written at least one prescription in the past 12 months.

READ LIST. ALLOW MULTIPLE RESPONSES.

Ativan (Lorazepam)	1
Depakote/Depakote ER/Depakote Sprinkle (Divalproex Sodium)	5
Dilantin (Phenytoin)	9
Keppra (Levetiracetam)	12
Lamictal (Lamotrigine)	14
Neurontin (Gabapentin)	19
Potiga (Ezogabine)	21
Topamax (Topiramate)	23
NONE OF THESE - TERMINATE	28

MUST SAY YES TO PUNCH 21 (POTIGA) TO BE CLASSIFIED AS A POTIGA PRESCRIBER. OTHERWISE, TERMINATE.

IF Q3 = PUNCH 4 (PHARMACY COM/RET) OR 5 (PHARMACY HOS/CLIN), ASK Q8.

- 8) I will now read you a list of medicines. Please tell me all of the medicines, if any, for which you have filled at least one prescription in the past 3 months.

READ LIST. ALLOW MULTIPLE RESPONSES.

Ativan (Lorazepam)	1
Carbatrol (Carbamazepine)	2
Celontin (Methsuximide)	3
Cerebyx (Fosphenytoin sodium)	4
Depakote/Depakote ER/Depakote Sprinkle (Divalproex Sodium)	5
Depacon (Valproate sodium)	6
Depakene (Valproic acid)	7
Diastat (Diazepam)	8
Dilantin (Phenytoin)	9
Felbatol (Felbamate)	10
Gabitril (Tiagabine hydrochloride)	11
Keppra (Levetiracetam)	12
Klonopin (Clonazepam)	13
Lamictal (Lamotrigine)	14
Lorazepam Intensol (Lorazepam)	15
Lyrica (Pregabalin)	16
Mebaral (Mephobarbital)	17
Mysoline (Primidone)	18
Neurontin (Gabapentin)	19
Peganone (Ethotoin)	20
Potiga (Ezogabine)	21
Tegretol/Tegretol XR (Carbamazepine)	22
Topamax (Topiramate)	23
Tranxene (Clorazepate dipotassium)	24
Trileptal (Oxcarbazepine)	25
Valium (Diazepam)	26
Zonegran (Zonisamide)	27
NONE OF THESE - TERMINATE	28

MUST SAY YES TO ANY IN ORDER TO CONTINUE; OTHERWISE, TERMINATE.

9) Do you normally wear corrective lenses, contacts, or glasses to read?

CONTINUE TO Q10a →	YES	1
SKIP TO Q10b →	NO	2

10a) Other than needing glasses or contacts to read, do you have any other visual impairment that would prevent you from being able to read on your own?

TERMINATE →	YES	1
SKIP TO INVITATION →	NO	2

10b) Do you have any visual impairment that would prevent you from being able to read on your own?

TERMINATE →	YES	1
CONTINUE →	NO	2

IF RESPONDENT MENTIONS HAVING ANY TROUBLE READING THEN TERMINATE, OTHERWISE CONTINUE.

INVITATION:

Thank you very much for your time today. We would like to invite you to participate in our research survey where we would ask you about current prescribing information and practices for a prescription product used to treat epilepsy. The survey is offered as an internet survey at your convenience and should take no more than 15-20 minutes to complete. Because we know your time is valuable, we will be offering an honorarium of \$X for completing the survey. Are you willing to participate?

SEE SCRIPT BELOW →	YES	1
QUALIFIED REFUSED →	NO	2

Thank you for your interest and willingness to participate in this survey.

IF INTERESTED, CONFIRM EMAIL ADDRESS. OFFER TELEPHONE OPTION IF REQUESTED.

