1. INTRODUCTION

POTIGA was approved with a FDA requirement for a Risk Evaluation and Mitigation Strategy (REMS). The goal of the REMS for POTIGA is to inform healthcare professionals of the risk of urinary retention and the symptoms of acute urinary retention in patients taking POTIGA. The REMS is comprised of a communication plan for healthcare professionals that is designed to disseminate information about the risk of urinary retention with POTIGA and highlight this potential risk and the need to inform patients to seek immediate medical attention for symptoms of urinary retention, inability to urinate, and/or pain with urination. There are two elements of the communication plan: (1) A Dear Healthcare Professional (HCP) Letter designed to disseminate information about the risk of urinary retention with POTIGA; letters are disseminated within 4 weeks of first retail availability (actual – May 7, 2012) and annually for the next two years (2) a REMS Program Website (available at time of launch; actual -April 16, 2012).

The target audience for these communications is: (1) Prescribing physicians i.e., Epileptologists, Neurologists and Neurosurgeons, (2) Pharmacists dispensing POTIGA tablets and the Medication Guide.

As a condition of approval, FDA requires that GlaxoSmithKline (GSK) assess the effectiveness of the communication plan. Accordingly, a survey will be conducted among a sample of prescribing physicians to evaluate whether they can recall the risk of urinary retention with POTIGA. In addition, the survey will evaluate where HCPs prefer to seek information for POTIGA, for example Dear HCP letters, website, or product labeling. The survey will concentrate on the risks described in the DHCP letter for POTIGA, though it is recognised that the DHCP letter is not the only source of information concerning risks associated with medication use. The design for this study is based on previous experience of risk management programs for GSK products.

A survey will also be conducted among a sample of pharmacists to evaluate whether they can recall the risk of urinary retention with POTIGA.

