4.2.2. Exclusion criteria

Physicians or pharmacists meeting any of the following criteria will not be eligible to take the survey:

- a. The physician or pharmacist is currently employed by, or is a representative of any of the following:
 - A A pharmaceutical company or manufacturer of medicines or healthcare products.
 - B Contributor/editor to published guideline committees for epilepsy or UR.
- b. The physician or pharmacist has a visual impairment that would prevent him or her from being able to read independently.
- c. The physician or pharmacist participated in the Pilot REMS study for POTIGA.
- d. The physician or pharmacist is an employee of GSK or Concentrics Research.

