5. STUDY ASSESSMENTS AND PROCEDURES

5.1. Screening and baseline assessments

Subjects participating in the pilot study will be removed programmatically from the sample list in order to avoid bias in the screener by specifically mentioning the drug name, even in a masked approach, during screening which may heighten awareness prior to the interview.

After accepting the initial recruitment invitation to participate in the study, individuals will be scheduled for a telephone screening interview. The screener will assess:

- Inclusion/exclusion criteria
 - The screener was amended after the study began to ask physicians a subset of epilepsy drugs at Q7 instead of the full list previously included. This subset still allows for masking of the drug to be studied (POTIGA), but shortens the burden on the physician to respond to the full listing during recruitment. This revision was made based on qualitative feedback during recruitment where physicians were not continuing with screening due to frustration with the length of this question. After reviewing data gathered to date, the most common responses to the drugs prescribed were included in the remaining listing, along with POTIGA.
 - Whether POTIGA has been prescribed within the past 12 months (physicians) or whether AEDs have been dispensed within the past 3 months (pharmacists).
 - Demographics: geographic region and type of healthcare provider. Additional prescribing or dispensing-related questions will be asked in the main survey questionnaire.

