5.2. Outcomes

Subject understanding of the risk of urinary retention and the symptoms of acute urinary retention associated with POTIGA will be assessed using the survey instrument.

The primary outcome of this study is the proportion of subjects that correctly respond to individual survey questions concerning the risk of urinary retention and the symptoms of acute urinary retention associated with POTIGA. The order in which potential responses to survey questions appear will be randomized. The proportion responding correctly will be tabulated separately for each item in the subject understanding survey instrument. These risks represent those described in the DHCP letter.

At the conclusion of the online survey, the final screen will display a summary of the relevant information from the POTIGA prescribing information, and a link to <http://www.potiga.com>. The phone respondents will be offered materials by email or the POTIGA website, but will also be given the toll-free number for the POTIGA response center [name] ([name]).

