We would also like to confirm that you are the [INSERT: physician/pharmacist] on record for this survey. Please select one of the following options:

- 1. I affirm that I am the same [INSERT: physician/pharmacist] who was screened and sent the survey passcode. [INSERT NAME]
- 2. I am not [INSERT NAME], but I work in this [INSERT: physician's office/pharmacy].

IF PUNCH 1 (SAME PHYSICIAN/PHARMACIST), CONTINUE.

IF PUNCH 2 (NOT PHYSICIAN OR PHARMACIST, BUT WORK IN SAME OFFICE/PHARMACY), SHOW SCREEN WITH MESSAGE: 'THANK YOU FOR YOUR TIME. UNFORTUNATELY, ONLY THE HEALTHCARE PROVIDER ON RECORD MAY PARTICIPATE IN THIS STUDY. IF YOU BELIEVE YOU HAVE RECEIVED THIS MESSAGE IN ERROR, PLEASE CONTACT [INSERT NAME & PHONE #] FOR FURTHER INSTRUCTIONS.' DO NOT ALLOW SUBJECT TO CONTINUE.

Survey

The following questions are being asked about your understanding of the prescribing information and practices related only to POTIGA (ezogabine). Please respond only about this medication, based on what you know at this time.

Please take your time and read each question carefully.

Please do not guess - if you do not know the answer, please just select 'I don't know'.

1. According to U.S. prescribing information, what is the FDA-approved indication for POTIGA? (Please select all that apply)

ALLOW MULTIPLE RESPONSES, EXCEPT PUNCH 4 OR 5.

Migraine	1
Partial-onset seizures	2
Generalized tonic clonic seizures	3
None of the above	4
I don't know	5

2. True or False: According to U.S. prescribing information, POTIGA can be used as monotherapy.

ALLOW ONE RESPONSE.

True	1
False	2
I don't know	3

3. According to U.S. prescribing information, which of the following are potential risks associated with POTIGA? (Please select all that apply)

ALLOW MULTIPLE RESPONSES, EXCEPT PUNCH 5 OR 6.

Urinary retention	1
Pancreatitis	2
Ischemic colitis	3
I don't know	4

4. According to U.S. prescribing information, what is the maximum recommended daily maintenance dose of POTIGA for the General Population?

ALLOW MULTIPLE RESPONSES, EXCEPT PUNCH 5 OR 6.

600mg	1
900mg	2
1200mg	3
2000mg	4
None of the above	5
I don't know	6

5. According to U.S. prescribing information, which of the following statements, if any, is true? (Please select all that apply)

ALLOW MULTIPLE RESPONSES, EXCEPT PUNCH 5 OR 6.

The oldest age at which POTIGA can be used is 65	1
There are no lower age limits for POTIGA	2
The youngest age at which POTIGA can be used is 12	3
The youngest age at which POTIGA can be used is 18	4

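### Screener Q2 item B names urinary retention to every candidate before the survey, which can bias upward the percent correct on survey Q3

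*Protocol*

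**What the plan says.** Section 4.2.2 excludes anyone who is a "Contributor/editor to published guideline committees for epilepsy or UR". The screener in Section 11.1 carries this out as Q2 item B, spelling out the abbreviation: "Contributor/editor to published guidelines committees for epilepsy or urinary retention". The interviewer's instruction is "READ LIST ONE AT A TIME". Q2 comes before the specialty question, so physicians and pharmacists both meet it. A list of medicines follows, then an invitation saying that the survey concerns an epilepsy product, without naming it. Section 7.1 restricts the analysis to people who passed the screener.

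Section 1 says the survey is to "evaluate whether they can recall the risk of urinary retention with POTIGA". Section 5.2 states: "The primary outcome of this study is the proportion of subjects that correctly respond to individual survey questions concerning the risk of urinary retention" (the sentence goes on to the symptoms of acute retention). Section 7.2 regards at least 80% correct on each question as sufficient understanding. Survey Q3 (Section 11.2) asks "which of the following are potential risks associated with POTIGA" and offers urinary retention, pancreatitis, ischemic colitis and a don't-know option.

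Section 5.1 removes pilot participants by program, so as to avoid "specifically mentioning the drug name, even in a masked approach, during screening which may heighten awareness prior to the interview". It adds that the shortened physician drug list still masks POTIGA. Section 9 lists representativeness and undetectable use of reference materials as limitations. It does not mention wording at screening.

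**The concern.** The protocol accepts that screening can prime a respondent and protects the drug name for that reason, but the screener discloses the condition the survey asks about. Urinary retention is the only adverse condition the screener mentions, and item B puts it beside epilepsy. When survey Q3 offers three conditions, a respondent who does not know the answer has met exactly one of them already.

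Survey Q3 is the item that most directly tests the REMS message. If part of its percent correct comes from the screener, the figure reported to FDA credits the communication plan with recall that the study itself supplied. Everyone analysed has passed the same item, so under the current screener there is no uncued group for comparison.

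**Working it through.** **Inputs.** From the protocol: 200 respondents per group (Protocol Summary), the 80% threshold (Section 7.2), and a margin of error of ±5.5 points at 80% with n = 200 (Section 8). Assumed: K, the true share aware of the risk, and c, the share of unaware respondents whom the cue moves to the correct answer. The protocol gives neither. I take urinary retention as the correct option in survey Q3, since Section 1 names it as the REMS risk.

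**Step 1: the plan's own figure.** Half-width = 1.96 × √(0.80 × 0.20 / 200) = 5.54 points, against 5.5 stated. It reproduces. It covers sampling error only, so it does not allow for a cue.

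**Step 2: which items are exposed.**

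| Survey item | What the question itself discloses | Room for the screener to add |
|---|---|---|
| Q3 | Urinary retention as one of three conditions | Yes: it singles out one option |
| Q7 | Urinary symptoms in the stem; follows Q3 | Doubtful |
| Q8 | Inability to pass urine in the stem | None evident |
| Q13 | Urinary retention in the stem | None |

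The items on indication, dose, age and food are unrelated to the cue.

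**Step 3: direction on Q3.** Observed proportion = K + (1 − K)c. Since c cannot be negative, the observed value is at least K. The lift, (1 − K)c, is larger where awareness is lower. That could matter more for pharmacists, who qualify by filling any AED and need not have dispensed POTIGA (Section 4.2.1).

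**Step 4: illustrations over assumed values.**

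The c needed for K to read as 80% is (0.80 − K)/(1 − K):
- K = 70%: 0.10/0.30 = 33%
- K = 75%: 0.05/0.25 = 20%
- K = 78%: 0.02/0.22 = 9%

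The true awareness behind an observed 80% is (0.80 − c)/(1 − c):
- c = 0: 80%
- c = 5%: 78.9%
- c = 10%: 77.8%
- c = 20%: 75.0%
- c = 30%: 71.4%

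The chance that at least 160 of 200 answer correctly when K = 75% (binomial tail at the observed proportion):

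| c | Observed proportion | Chance of reaching 80% |
|---|---|---|
| 0 | 75.0% | 5.8% |
| 5% | 76.25% | 12.1% |
| 10% | 77.5% | 22.5% |
| 20% | 80.0% | 54.2% |
| 30% | 82.5% | 84.7% |

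These rows show how sensitive the threshold is to a cue. They are not evidence that anyone uses it.

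**The case against.** The strongest reply is that the cue is faint. It is half of one item in a three-item affiliation list and is tied to no drug. POTIGA is one of 8 medicines read to physicians and one of 27 read to pharmacists, and the invitation names no product. To benefit, a respondent must later connect an affiliation question with POTIGA. The questionnaire also tells respondents not to guess and offers a don't-know option on Q3. All of this stands, and it means c could be close to zero. It does not change the direction, and it does not explain why the drug is masked while the risk is named.

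Three stronger readings are tempting and are not supported:

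- *That all the voiding items are inflated.* Q13 states the condition itself, and the screener says nothing about which patient groups need closer monitoring. Q7 already refers to urinary symptoms and comes after Q3 has shown the term to everyone.
- *That the gap between screening and an emailed survey lets respondents look the answer up.* In that gap they have not been told which drug is studied. Once the survey names POTIGA, an online respondent can look up its risks with or without the cue, and Section 9 already concedes that this cannot be detected.
- *That the screener demonstrably raises the result by several points.* The protocol contains nothing from which c could be estimated.

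It is also fair that the study is descriptive, with no formal testing. Even so, Section 7.2 reads each question against a fixed 80% line, so a one-sided bias on Q3 matters.

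**Conclusion.** The point holds for survey Q3 and for direction only. The screener names the risk to everyone who can enter the analysis, and any resulting bias in the percent correct on Q3 is upward. Its size is unknown: nothing if no unaware respondent uses the cue, and 5 points if true awareness is 75% and one in five of the unaware do. Both of those values are assumptions.

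The protocol's precision figure is correct but does not cover this bias. Reading aloud fits the telephone screening of Sections 3.2 and 5.1; under the email and fax routes of Section 3.1 the same words would be seen, so exposure does not depend on the route.

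A reader might infer that a Q3 result above 80% would be worthless. The documents do not support that. They support correcting the wording and disclosing the cue. This should be fixed, but it does not invalidate the survey.

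**What to change.** For all further screening, do one of the following:

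1. Delete the reference to urinary retention from screener Q2 item B and align exclusion a.B in Section 4.2.2. Cost: a very few contributors to urinary-retention guidelines might enter. That risk is small, because Section 1 records that urologists are no longer targeted.
2. Keep the phrase but place it among several unrelated conditions. Eligibility stays as it is. Cost: a slightly longer item, and the cue is diluted, not removed.

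Either is preferable to excluding contributors to any clinical guideline, which would narrow eligibility when Section 3.2 reports recruitment well below expectation.

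Sections 3.2 and 5.1 show that the study has started, and the only screener change they describe is to the physician drug list. New wording therefore cannot help those already screened. For them, record the screener version, tabulate survey Q3 by version within each group, and add the cue to Section 9.

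That tabulation is descriptive. The versions would be separated in time, and the letters are repeated annually (Section 1), so a difference need not be due to the wording. It would also be imprecise. If a group of 200 split evenly (an assumption), the 95% half-width for the difference near 80% would be 1.96 × √(2 × 0.80 × 0.20 / 100) = 11.1 points, so a lift of about 5 points could not be confirmed or ruled out. The limitation should therefore be stated whatever the table shows.

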11.2. Questionnaire

PHYSICIAN/PHARMACIST ASSESSMENT

Quantitative Questionnaire

All programming notes are presented in **BOLD CAPS** throughout the document. These are instructions only and will not be visible to respondents in the survey.

The following are the sections of the survey and items included in this document:

- Introduction
- Screener Profile
- Confidentiality & Consent Agreement
- Physician Assessment Survey
- Additional Demographic Profile

Introduction

Thank you for your interest in participating in our research survey. Your time and opinions are greatly valued, as your responses will help us better understand the perspectives of physicians and pharmacists such as yourself.

This survey is being conducted to evaluate your understanding of prescribing information and practice habits related to a medication used to treat epilepsy. Please be assured that your individual answers will be kept strictly confidential. This survey will take approximately 15-20 minutes to complete.

Screener Profile

We would like to begin by re-confirming 1-2 questions about you.

A. How would you classify your primary specialty? **ALLOW ONE RESPONSE.**

CONTINUE TO QB	Neurology	1
CONTINUE TO QB	Neurosurgery	2
CONTINUE TO QB	Epileptology	3
SKIP TO QD	Pharmacy (Community/Retail)	4
SKIP TO QD	Pharmacy (Hospital/Clinical)	5
TERMINATE	Other (Specify)	6

ASK QB ONLY IF QA = PUNCH 1, 2, OR 3.

B. Approximately how many patients have you prescribed AEDs for in the past 12 months? **ALLOW ONE RESPONSE.**

None TERMINATE	1
1-2	2
3-10	3
11-20	4
More than 20 patients	5

ASK QC ONLY IF QA = PUNCH 1, 2, OR 3.

C. Please confirm which of the following medicines, if any, you have written at least one prescription for in the past 12 months. **READ LIST. ALLOW MULTIPLE RESPONSES.**

Lamictal (Lamotrigine)	1
Lyrica (Pregabalin)	2
Potiga (Ezogabine)	3
Tegretol/Tegretol XR (Carbamazepine)	4
Topamax (Topiramate)	5
None of the above TERMINATE	6

TERMINATE IF PUNCH 3 (POTIGA) NOT SELECTED.

ASK QD ONLY IF QA = PUNCH 4 OR 5.

D. Approximately how many prescriptions for AEDs have you filled in the past 3 months? **ALLOW ONE RESPONSE.**

None TERMINATE	1
1-2	2
3-10	3
11-20	4
More than 20 prescriptions	5

Thank you. Based on your responses, you qualify for the survey. In order to participate, you will need to read and electronically sign a Confidentiality & Consent Agreement on the following pages.

We would also like to confirm that you are the [INSERT: physician/pharmacist] on record for this survey. Please select one of the following options:

- 1. I affirm that I am the same [INSERT: physician/pharmacist] who was screened and sent the survey passcode. [INSERT NAME]
- 2. I am not [INSERT NAME], but I work in this [INSERT: physician's office/pharmacy].

IF PUNCH 1 (SAME PHYSICIAN/PHARMACIST), CONTINUE.

IF PUNCH 2 (NOT PHYSICIAN OR PHARMACIST, BUT WORK IN SAME OFFICE/PHARMACY), SHOW SCREEN WITH MESSAGE: 'THANK YOU FOR YOUR TIME. UNFORTUNATELY, ONLY THE HEALTHCARE PROVIDER ON RECORD MAY PARTICIPATE IN THIS STUDY. IF YOU BELIEVE YOU HAVE RECEIVED THIS MESSAGE IN ERROR, PLEASE CONTACT [INSERT NAME & PHONE #] FOR FURTHER INSTRUCTIONS.' DO NOT ALLOW SUBJECT TO CONTINUE.

Survey

The following questions are being asked about your understanding of the prescribing information and practices related only to POTIGA (ezogabine). Please respond only about this medication, based on what you know at this time.

Please take your time and read each question carefully.

Please do not guess - if you do not know the answer, please just select 'I don't know'.

1. According to U.S. prescribing information, what is the FDA-approved indication for POTIGA? (Please select all that apply)

ALLOW MULTIPLE RESPONSES, EXCEPT PUNCH 4 OR 5.

Migraine	1
Partial-onset seizures	2
Generalized tonic clonic seizures	3
None of the above	4
I don't know	5

2. True or False: According to U.S. prescribing information, POTIGA can be used as monotherapy.

ALLOW ONE RESPONSE.

True	1
False	2
I don't know	3

3. According to U.S. prescribing information, which of the following are potential risks associated with POTIGA? (Please select all that apply)

ALLOW MULTIPLE RESPONSES, EXCEPT PUNCH 5 OR 6.

Urinary retention	1
Pancreatitis	2
Ischemic colitis	3
I don't know	4

4. According to U.S. prescribing information, what is the maximum recommended daily maintenance dose of POTIGA for the General Population?

ALLOW MULTIPLE RESPONSES, EXCEPT PUNCH 5 OR 6.

600mg	1
900mg	2
1200mg	3
2000mg	4
None of the above	5
I don't know	6

5. According to U.S. prescribing information, which of the following statements, if any, is true? (Please select all that apply)

ALLOW MULTIPLE RESPONSES, EXCEPT PUNCH 5 OR 6.

The oldest age at which POTIGA can be used is 65	1
There are no lower age limits for POTIGA	2
The youngest age at which POTIGA can be used is 12	3
The youngest age at which POTIGA can be used is 18	4
None of the above	5
I don't know	6

6. According to U.S. prescribing information, which of the following statements, if any, is true? (Please select all that apply)

ALLOW MULTIPLE RESPONSES, EXCEPT PUNCH 4 OR 5.

POTIGA should always be taken with food	1
POTIGA should always be taken on its own, without food	2
POTIGA can be taken with or without food	3
None of the above	4
I don't know	5

7. Which of the following urinary symptoms, if any, should you specifically advise patients taking POTIGA to watch out for? (Please select all that apply)

ALLOW MULTIPLE RESPONSES, EXCEPT PUNCH 5 OR 6.

Pain when urinating	1
Difficulty starting urination	2
Renal colic	3
Inability to urinate	4
None of the above	5
I don't know	6

8. If a patient on POTIGA experiences inability to pass urine, what would you advise them to do? (Please select all that apply)

ALLOW MULTIPLE RESPONSES, EXCEPT PUNCH 5 OR 6.

Report the issue at their next doctor's appointment	1
Drink more water	2
Seek immediate medical attention	3
Stop taking POTIGA	4
None of the above	5
I don't know	6

9. According to U.S. prescribing information, when increasing the dose, what is the maximum total daily dose at which POTIGA can be increased once every 7 days?

ALLOW MULTIPLE RESPONSES, EXCEPT PUNCH 5 OR 6.

Total daily dose increased by 50mg/day	1
Total daily dose increased by 150mg/day	2
Total daily dose increased by 200mg/day	3
Total daily dose increased by 300mg/day	4
None of the above	5
I don't know	6

10. True or False: According to U.S. prescribing information, for the General Population, the recommended total initial dosage should be 150mg per day for one week.

ALLOW ONE RESPONSE.

True	1
False	2
I don't know	3

11. The label for POTIGA recommends caution when prescribing for patients with which of the following conditions, if any?

		Yes	No	Don't Know
A	Moderate to severe renal or hepatic impairment	1	2	3
B	Moderate to severe Crohn's disease	1	2	3
C	Moderate to severe asthma	1	2	3
D	Patients over the age of 65 years	1	2	3
E	Moderate to severe glaucoma	1	2	3

12. True or False: It is known from controlled studies that adverse events related to voiding dysfunction generally tend to be reported within the first 6 months after starting POTIGA.

ALLOW ONE RESPONSE.

True	1
False	2
I don't know	3

13. Which of the following patient groups are recommended to have closer monitoring (including comprehensive evaluation of urologic symptoms) for urinary retention? (Please select all that apply)

ALLOW MULTIPLE RESPONSES, EXCEPT PUNCH 6 OR 7.

Patients with benign prostatic hyperplasia (BPH)	1
Patients who are unable to communicate clinical symptoms (e.g. cognitively impaired patients)	2
Patients who use concomitant medications that may affect voiding (e.g. anti-cholinergics)	3
Patients who use non-steroidal anti-inflammatory drugs (NSAIDs)	4
Patients who are obese	5
None of the above	6
I don't know	7

SHOW SECTION B ONLY IF ANY RESPONSES (Q1-13) WERE INCORRECT

SECTION B: For the next set of questions, I'd like to ask you to provide some further information on some of your responses. Please provide as much detail of your thought process as possible when responding.

SHOW Q1_1 THROUGH Q13_1 ONLY FOR ANY INCORRECT RESPONSES AT Q1-13. THESE ARE OPTIONAL QUESTIONS. SHOW QUESTION TEXT FOR EACH, THEN THE QUESTION (1_1 – 13_1).

1_1) Previously, at Question 1, you responded [INSERT Q1 RESPONSE]. What led you to choose that response?

2_1) Previously, at Question 2, you responded [INSERT Q2 RESPONSE]. What led you to choose that response?

3_1) Previously, at Question 3, you responded [INSERT Q3 RESPONSE]. What led you to choose that response?

4_1) Previously, at Question 4, you responded [INSERT Q4 RESPONSE]. What led you to choose that response?

5_1) Previously, at Question 5, you responded [INSERT Q4 RESPONSE]. What led you to choose that response?

6_1) Previously, at Question 6, you responded [INSERT Q6 RESPONSE]. What led you to choose that response?

7_1) Previously, at Question 7, you responded [INSERT Q7 RESPONSE]. What led you to choose that response?

8_1) Previously, at Question 8, you responded [INSERT Q8 RESPONSE]. What led you to choose that response?

9_1) Previously, at Question 9, you responded [INSERT Q9 RESPONSE]. What led you to choose that response?

10_1) Previously, at Question 10, you responded [INSERT Q10 RESPONSE]. What led you to choose that response?

11_1) Previously, at Question 11, you responded [INSERT Q11 RESPONSE]. What led you to choose that response?

12_1) Previously, at Question 12, you responded [INSERT Q12 RESPONSE]. What led you to choose that response?

13_1) Previously, at Question 13, you responded [INSERT Q13 RESPONSE]. What led you to choose that response?

SKIP TO DEMOGRAPHICS (B) IF QA = PUNCH 4 OR 5. CONTINUE TO DEMOGRAPHICS (A) IF QA = PUNCH 1, 2 OR 3.

DEMOGRAPHICS (A)

The next sets of questions are about your practice history so that we can group your responses with others like you.

14. How long have you been practicing medicine?

ALLOW ONE RESPONSE.

Less than 5 years	1
5-15 years	2
16-25 years	3
26-35 years	4
More than 35 years	5

15. How long have you been prescribing anti-epileptic drugs (AEDs)?

ALLOW ONE RESPONSE.

Less than 5 years	1
5-15 years	2
16-25 years	3
26-35 years	4
More than 35 years	5

16. How many months have you been prescribing POTIGA?

ALLOW ONE RESPONSE.

Less than 1	1
1-3	2
4-6	3
7-9	4
10-12	5
More than 12 months	6
I don't know/don't remember	7

17. Approximately how many patients have you prescribed POTIGA for in the past 12 months?

ALLOW ONE RESPONSE.

1-2	1
3-10	2
11-20	3
More than 20 patients	4

18. On a monthly basis, approximately how many prescriptions for AEDs (including new prescriptions and refills) have you written in the past 12 months?

ALLOW ONE RESPONSE

1-10	1
11-30	2
31-50	3
More than 50	4

19. What is the age range of your current patient population? Please select all categories that you treat.

ALLOW MULTIPLE RESPONSES.

Pediatric (Under 18)	1
18-34	2
35-64	3
65 +	4

20. Approximately what is the size of your current total patient population?

ALLOW ONE RESPONSE.

Less than 100 patients	1
100 – 500 patients	2
501 – 1000 patients	3
More than 1000 patients	4

21. Approximately what is the size of your current epilepsy patient population?

ALLOW ONE RESPONSE.

Less than 10 patients	1
10 – 50 patients	2
51 – 100 patients	3
101+ patients	4
I do not treat patients with epilepsy	5

SKIP TO SECTION C IF QA = PUNCH 1, 2 OR 3. CONTINUE TO DEMOGRAPHICS (B) IF QA = PUNCH 4 OR 5.

DEMOGRAPHICS (B)

The next sets of questions are about your pharmacy history so that we can group your responses with others like you.

22. How long have you been a practicing pharmacist?

ALLOW ONE RESPONSE.

Less than 5 years	1
5-15 years	2
16-25 years	3
26-35 years	4
More than 35 years	5

23. How long have you been dispensing and/or answering patient questions regarding prescribed AEDs?

ALLOW ONE RESPONSE.

Less than 5 years	1
5-15 years	2
16-25 years	3
26-35 years	4
More than 35 years	5

24. Have you answered any patient questions related to POTIGA in the past 12 months?

ALLOW ONE RESPONSE.

Yes	1
No	2
I don't know/don't remember	3

25. Have you dispensed POTIGA in the past 12 months?

ALLOW ONE RESPONSE.

Yes	1
No	2
I don't know/don't remember	3

IF Q25 IS NO OR DK/DR, SKIP TO Q28.

26. How many months have you been dispensing POTIGA?

ALLOW ONE RESPONSE.

Less than 1	1
1-3	2
4-6	3
7-9	4
10-12	5
More than 12 months	6
I don't know/don't remember	7

27. Approximately how many patients have you dispensed POTIGA for in the past 12 months?

ALLOW ONE RESPONSE.

1-2	1
3-10	2
11-20	3
More than 20 patients	4
I don't know/don't remember	5

28. On a monthly basis, approximately how many prescriptions for anti-epileptic drugs (AEDs) (including new prescriptions and refills) have you filled in the past 12 months?

ALLOW ONE RESPONSE.

1 – 10	1
11 – 30	2
31 – 50	3
More than 50 prescriptions	4

SECTION C: The remaining questions are about your own personal experience, specifically regarding your awareness, receipt and dissemination of information about POTIGA.

29. Have you learned about the risks associated with use of POTIGA from any of the following sources?

	Yes	No	Don't
POTIGA Dear HCP Letter	1	2	3
GlaxoSmithKline Medical Information	1	2	3
Other Healthcare Professionals	1	2	3
GlaxoSmithKline Promotional Materials	1	2	3
GSK Website: POTIGA.com	1	2	3
GlaxoSmithKline Sales Representatives	1	2	3
GlaxoSmithKline-sponsored Educational Meeting	1	2	3
POTIGA Product Labeling (including Prescribing Information, Medication Guide)	1	2	3

30. How would you prefer to learn about the risks associated with use of POTIGA in the future? Please select up to 3 options.

POTIGA Dear HCP Letter	
GlaxoSmithKline Medical Information	
Other Healthcare Professionals	
GlaxoSmithKline Promotional Materials	
GSK Website: POTIGA.com	
GlaxoSmithKline Sales Representatives	
GlaxoSmithKline-sponsored Educational Meeting	
POTIGA Product Labeling (including Prescribing Information, Medication Guide)	

CLOSING: Those are all of our questions. Thank you very much for your time and for sharing your responses with us today. As you may know, medication manufacturers conduct surveys, such as this one, from time to time to learn how well they have communicated to healthcare providers regarding the risks that may be associated with that medication.

We would now like for you to take a moment to review some important information about POTIGA. This information can be found in the Prescribing Information, which can be found online at:
http://us.gsk.com/products/assets/us_potiga.pdf

The Dear Healthcare Professional Letters (for prescribing physicians and pharmacists) can be found online at:

Prescribing Physicians:

https://www.gsksource.com/gskprm/en/US/images/gsk_content/POTIGA/PGA056R0_RMS_HCP_Letter_DC.pdf

Pharmacists:

https://www.gsksource.com/gskprm/en/US/images/gsk_content/POTIGA/PGA055R0_RMS_PharmLetter_DC.pdf

